# 2.2 Violations and deviations

An Important Protocol Deviation, per ICH definition is "a subset of protocol deviations that may significantly impact the completeness, accuracy, and/or reliability of the study data or that may significantly affect a participant's rights, safety, or wellbeing."

The list of study specific IPDs is provided in the AstraZeneca Protocol Deviations Plan (PDP).

In addition, all protocol deviations and major issues related to COVID-19 will be captured with the prefix "COVID19" for CSR reporting.

# **3 PRIMARY AND SECONDARY VARIABLES**

# **3.1 General principles**

# **3.1.1 Definition of baseline**

In general, the last measurement prior to first injection of IP will serve as the baseline measurement for efficacy and safety endpoints. If Visit 3 (Week 0) measurement is missing, the last non-missing value before Visit 3 (Week 0) will be used as baseline instead. If there is no result collected prior to Visit 3, then baseline value will be set to missing and will not be imputed. In the scenario where there are two assessments on Visit 3 (Week 0) prior to first

dose, one with time recorded and the other without time recorded, the one with time recorded would be selected as baseline.

An exception from the general rule will be ECGs - the mean value of each parameter from the repeated pre-dose measurements at Visit 3 (Week 0) will be recorded in eCRF and used as the baseline value.

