# Order of procedures:

- All assessments should be performed prior to a munistration of investigational product except where otherwise indicated (eg, post-de ev al signs)
- AO assessments should take pince before spirometry.
- Sputum samples should be taken are requiring a BD withhold (including spirometry and AO).
- If both nasal epitheranding fluid and mucosal samples are required on the same day then the epithelial lining fluid sample should be taken prior to the mucosal sample.

Refer to Section 8 for additional information on assessment ordering (eg, pre-, post-dose or multiple timepoints within a visit).

 Table 2
 Screening Procedures

Study Period	Screen	ing / Run-in
Visit Number	SV1	SV2
Procedure / Study Day	Day -35 to Day -28	Day -21 to Day -7
Study Week	Week -5 to -4	Week -3 to -1
Written informed consent/assignment of E-code a	X	
Written informed consent for future use and/or genetic analysis (optional) a	X	
Written informed consent for CT sub-study (as applicable) a	X	
Verify eligibility criteria	X	X
Safety Assessments		
Demography	X	
Medical and COPD/chronic bronchitis history including assessment of COPD exacerbations and evaluation of predominant emphysema by physician diagnosis	x	
Smoking History	X	
Physical examination (full)	X	
Weight, height	X	
ECG	X	
Vital signs	X	
Assessment of AEs/SAEs	X	X
Concomitant medications	X	X
Echocardiogram a, b		X
CT a, b, c		X
SARS-CoV-2 nucleic acid test (nasopharyngeal swab or salivary sample) d	X	X
Efficacy assessments		
Clinic Spirometry (pre-BD)	X	
Clinic Spirometry (post-BD)	X	
Airwave oscillometry		X
Provision, and training on use, of at home spirometer and eDiary for use every day	X	
Assess adherence to the completion of eDiary entries and home device use		X
Provision of and training of use of cough monitoring followed by 24 hour monitoring post clinical visit		X

AstraZeneca

 Table 2
 Screening Procedures

Study Period	Screen	ing / Run-in
Visit Number	SV1	SV2
Procedure / Study Day	Day -35 to Day -28	Day -21 to Day -7
Study Week	Week -5 to -4	Week -3 to -1
On-site ePROs:		
CAT	X	
Collect blood for:		
Serum chemistry	X	
NT-proBNP	X	
Haematology	X	
Coagulation parameters	X	
Hepatitis B, C; HIV-1; virology	X	
Serum pregnancy test (female participants of childbearing potential only)	X	
FSH (if needed to confirm post-menopausal status in female participants aged < 50 years)	X	
IGRA (TB test)	X	
Collect other samples:		
CCI		
Collect urine for:		

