  - (c) A diagnosis of asthma made when the subject was aged ≥ 40 years, confirmed by the investigator to be a misdiagnosis after discussion with and agreement of the AstraZeneca Study Physician.
- 6 Clinically important pulmonary disease other than COPD (eg, active lung infection, clinically significant bronchiectasis, pulmonary fibrosis, cystic fibrosis, hypoventilation syndrome associated with obesity, lung cancer, alpha-1 anti-trypsin deficiency and primary ciliary dyskinesia) or another diagnosed pulmonary or systemic disease that is associated with elevated peripheral eosinophil counts (eg, allergic bronchopulmonary aspergillosis/mycosis, Churg-Strauss syndrome, hypereosinophilic syndrome),

- radiological findings, and/or laboratory findings suggestive of a respiratory disease other than COPD that is contributing to the participant's respiratory symptoms.
- Increased pre-BD FEV1 at randomization visit (SV3) compared to Screening SV1 of  $\geq$  400 mL or  $\geq$  25% of SV1 FEV1.
- 8 Known history of allergy or reaction to any component of the study intervention formulation, including hereditary fructose intolerance.
- Any other clinically relevant abnormal findings on physical examination, laboratory testing including hematology, coagulation, serum chemistry, or urinalysis; or chest CT scan at screening or randomization, which in the opinion of the investigator or medical monitor may compromise the safety of the participant in the study or interfere with evaluation of the study intervention or reduce the participant's ability to participate in the study. Abnormal findings include, but are not limited to:
  - (a) ALT or AST  $> 2 \times ULN$ .
  - (b) TBL  $> 2 \times$  ULN (unless due to Gilbert's diseas)
  - (c) Evidence of chronic liver disease
  - (d) Abnormal vital signs, after 10 minutes of being in a comfortable supine position (confirmed by 1 controlled measurement), usefined as any of the following:
    - (i) Systolic BP < 80 mmHg or  $\ge 150$  mmHg.
    - (ii) Diastolic BP  $< 50 \text{ mmHg or } \ge 95 \text{ mmHg.}$
    - (iii) Pulse < 45 or > 100 beat per minute.
  - (e) This exclusion criterion has been removed.
  - (f) Any clinically significant Yvthm, conduction, or morphology abnormalities in the 12-lead ECG including bu not imited to corrected QT interval (Fridericia) (Vandenberk et al 201c) > 450 ms.
  - (g) Chest CT scan tino ... requiring further investigation or repeat CT surveillance before SV14.

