# 1.3 Number of participants

A sample size of 140 participants (70 participants per arm) will provide 80% power to detect a difference in mean change from baseline in FEV1 at Week 12 of 90 mL (assumed SD of 250 mL) between the 2 randomized groups at a one-sided 10% level of statistical significance. To allow for 2% of participants being ineligible for the primary analysis, approximately 144 participants will be randomized in the study (72 per arm).

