# 4.1.2 Repeated measures mixed effects analysis of covariance model

The repeated measures mixed effects analysis of covariance model (MMRM) will be used to fit change from baseline for continuous endpoints at each visit, for the ITT population. For Primary Analysis, the model will include all available data from all visits up to and including Week 12, irrespective of whether the participant discontinued study intervention. Since a repeated measures model is being applied, no imputation will be made for missing data. The model will include fixed effects for baseline, log-transformed eosinophil value, background medication strata, geographical region, number of exacerbations during the previous 12 months ( $\leq$ 1 vs 2 or more), visit, study intervention and the baseline by visit and study intervention by visit interactions. An unstructured covariance matrix will be used to describe the correlations between observations on a participant between visits, and Kenward-Roger correction will be used for degrees of freedom approximation in the generation of model. In

the event that the model with unstructured covariance matrix fails to converge, and alternative such as autoregressive or compound symmetry will be used instead. Estimates of the least square mean change from baseline in  $FEV_1$  for each study intervention, and the difference between them (MEDI3506-placebo), together with two-sided 80% CI, will be obtained from the model for each visit. The significance of the study intervention effect will be tested at a 10% one-sided level of significance.

The reportable results from the model will be:

- The least-square means (LSMeans) change from baseline at each visit and their standard errors for each study intervention group
- The difference in change from baseline at certain visit between MEDI3506 and placebo (LSMeans difference) together with its two-sided 80% confidence interval (CI)
- The one-sided p-value for the difference in change from baseline at each visit between MEDI3506 and placebo

If the parameter is log-normally distributed, the variable fitted in the model will be the change from baseline in logarithmical scale, with the logarithm of the baseline value as a covariate. Change from baseline in logarithmical scale is defined as the log-transformation of the postbaseline visit value minus the log-transformation of the baseline value.

The MMRM will be as described above but the reportable results from the model will be:

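### The primary FEV1 model leaves out the SV1 pre-bronchodilator reading that eligibility already requires: a modest loss of efficiency of uncertain size, not a bias

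*SAP*

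**What the plan says.** **Baseline.** SAP 3.1.1: "the last measurement prior to first injection of IP will serve as the baseline measurement for efficacy and safety endpoints". An earlier value is used only if the SV3 value is missing.

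**Model.** SAP 4.1.2: "The model will include fixed effects for baseline, log-transformed eosinophil value, background medication strata, geographical region", followed by prior exacerbations, visit, treatment, and the baseline-by-visit and treatment-by-visit interactions. There is one baseline term. Neither the supportive analysis (4.2.4.2) nor the sensitivity analyses (4.2.4.3) add an SV1 term. Some text in SAP 3.3.1 is redacted, but the covariate list in 4.1.2 is visible in full.

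**Data collected.** Protocol Table 2 schedules the row beginning "Clinic Spirometry (pre-BD" at SV1 (Day -35 to Day -28). Table 3 schedules the same test at SV3. Protocol 5.2, Exclusion 7, excludes a rise in pre-bronchodilator FEV1 "at randomization visit (SV3) compared to Screening SV1 of" at least 400 mL or at least 25% of the SV1 value.

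**Sample size.** SAP 1.3: "A sample size of 140 participants (70 participants per arm) will provide 80% power to detect a" difference "at Week 12 of 90 mL" ("assumed SD of 250 mL") at a "one-sided 10% level of statistical significance".

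**The concern.** A single spirometry reading contains visit-to-visit noise. When only that reading is adjusted for, part of its noise remains in the residual variance of the treatment comparison. A second reading taken before randomisation helps whenever it still predicts Week 12 FEV1 once SV3 is known, and a stable personal level measured with noise implies that it does.

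The SV1 reading is already in the database. Exclusion 7 needs it, Protocol Section 5 allows no eligibility waivers, and spirometry is not among the tests that Protocol 5.4 lets a rescreened participant carry over. Elsewhere the SAP does average out noise at baseline: ECG baselines are means of repeats, and diary baselines are 14-day averages.

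At stake is the precision of the primary test, which is planned at 80% power and gates the key secondary endpoints (SAP 4.1.1).

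**Working it through.** **1. The plan's own figure.** Inputs from SAP 1.3: difference 90 mL, SD 250 mL, one-sided 10%, 80% power.

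n per arm = 2(1.2816 + 0.8416)² × (250/90)² = 69.6, so 70 per arm and 140 in total. Power at 70 per arm = Φ(90/(250√(2/70)) − 1.2816) = Φ(0.848) = 80.2% (80.0% by the exact t calculation). 70/0.98 = 71.4, so 72 per arm and 144 in total. The plan's figures reproduce.

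**2. Measure of gain.** Let f = Var(Week 12 | SV3, SV1) / Var(Week 12 | SV3). Power with SV1 added uses SD = 250√f, taking 250 mL as the residual SD of the planned model.

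**3. Assumptions.** The documents give no correlation between visits. Assume a between-participant SD of 450–600 mL and a noise SD of s per visit, and let true change between SV3 and Week 12 have variance τ² = 250² − 2s². SV1 is taken as 32 days before SV3, and Week 12 (Day 85) is 84 days after it. There are two cases:
- A: no true within-person change between SV1 and SV3.
- B: true change accrues at the same rate before SV3, with variance τ² × 32/84.

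**4. Worked example: between-participant SD 600, s = 120.** τ² = 62,500 − 28,800 = 33,700.

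Case A, SV3 only: 408,100 − 360,000²/374,400 = 61,946 (SD 248.9 mL). With SV1 added, the mean of the two readings carries half the noise variance: 408,100 − 360,000²/367,200 = 55,159 (SD 234.9 mL). So f = 0.890, and power is 83.5%.

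Case B: the variance accrued before SV3 is 33,700 × 32/84 = 12,838. The residual SD goes from 248.9 to 239.7 mL, so f = 0.927 and power is 82.4%.

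**5. Range over noise SD** (spread is over between-participant SD 450–600 mL).

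| Noise SD (mL) | Variance cut, A | Power, A | Variance cut, B | Power, B |
|---|---|---|---|---|
| 50 | 2.0% | 80.8% | 0.3% | 80.3% |
| 80 | 4.9–5.0% | 81.7% | 1.8–1.9% | 80.7–80.8% |
| 120 | 10.5–11.0% | 83.4–83.5% | 6.8–7.3% | 82.2–82.4% |
| 150 | 15.9–16.8% | 85.1–85.4% | 13.4–14.3% | 84.3–84.6% |
| 175 | 21.1–22.5% | 86.8–87.2% | 20.9–22.3% | 86.7–87.2% |

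The last row needs almost all of the 250 mL to be noise: 2 × 175² = 61,250 of 62,500.

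**6. Other correlation structures.** Under equal correlation ρ, f = (1 + 2ρ)/(1 + ρ)². ρ = 0.5 gives 0.889 (power 83.6%) and ρ = 0.8 gives 0.802 (86.3%). If all within-person variation is slow drift around a stable personal level, with no noise, f is about 0.96–0.98 and power about 81%. For a pure first-order autoregressive process f = 1, and nothing is gained.

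**7. Effect of Exclusion 7.** A simulation that removed participants breaching Exclusion 7 (assumed mean FEV1 1,300 mL) gave f = 0.85–0.98 and power of about 81–85%.

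**The case against.** The strongest reply is that nothing in the plan is wrong. Adjusting for the last pre-dose value with a baseline-by-visit term is a valid analysis, and 70 per arm reproduces. That stands in full. A reader might infer that the trial is underpowered or the comparison biased; the documents support neither.

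A reader might also infer a dependable gain of several points of power. The documents do not support that either, because the larger figures need either little true change between SV1 and SV3 or mostly measurement noise, and no visit correlations are given. SV1 is also somewhat less comparable with Week 12 than SV3 is: later spirometry must fall within 1.5 hours of the SV3 time, while SV1 need only fall between 6:00 and 11:00 AM (Protocol 8.1.1.1). Exclusion 7 trims the gain further.

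Nor is it established that the primary test has no reserve. SAP 1.3 does not say whether 250 mL is the SD of raw change or a residual SD. If it is raw change, then at ρ = 0.8 the planned model already has 83.2% power (residual SD 237.2 mL), and adding SV1 gives 89.0% (212.5 mL).

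Finally, the change is not entirely free or free of missing data. Rescreened participants may have two SV1 readings, a protocol deviation could leave SV1 missing, and a missing covariate would drop that participant from the model. Nor does the change carry over to post-bronchodilator spirometry, which is not done at SV3 (Protocol Table 3) and already takes SV1 as its baseline visit (SAP Table 16). These points stand and limit the fix.

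**Conclusion.** The point holds as one of efficiency. A pre-randomisation reading of the primary outcome variable, required by eligibility, is unused in the primary model except as a fallback. Treatment cannot affect it, so adjusting for it does not bias the comparison.

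The expected cut in residual variance is about 0.3% to 22%, with power of about 80–87% against the planned 80%, or about 81–85% with Exclusion 7 simulated. All of these figures rest on assumed variance components. The upper end requires within-visit noise to dominate; if slow drift dominates, the gain is close to nil. The change is still worth making, because the possible gain is useful and the cost is small.

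**What to change.** Before any unblinding (including an administrative interim analysis), amend SAP 4.1.2 and log the change in SAP Section 6:

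- For the pre-bronchodilator FEV1 model, and likewise pre-bronchodilator FVC, add the SV1 value of the same parameter and SV1-by-visit as fixed effects beside the SV3 baseline and baseline-by-visit.
- Keep the endpoint as change from the SV3 baseline, and keep the one-baseline model as a sensitivity analysis.
- Leave the post-bronchodilator models as they are.
- For rescreened participants, use SV1 from the screening that led to randomisation.
- State a rule for a missing SV1 value, for example a single mean fill-in that ignores treatment arm, so that nobody is dropped. State also that where SV3 is missing and SAP 3.1.1 substitutes SV1, the same value serves in both terms.

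The cost is one parameter per visit: four in the Week 12 model (Weeks 2, 4, 8 and 12), or about one degree of freedom at Week 12, and ten in the Week 36 model. SAP 3.1.9 allows subgroups down to 15% of participants, about 21 people (0.15 × 140), so the term can be left out of small-subgroup models. No new data are needed. SAP Section 6 already adds region and prior exacerbations to the protocol's model, so a further pre-randomisation covariate is in keeping with the plan.

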#### For

BCSS score,

E-RS:COPD score, Cough VAS, CCI baseline would be defined as the average from last 2 weeks (14 days) results prior to first dose of investigational product (Visit 3), ie, from evening of Study Day -14 to the morning of Study Day 1. If there are fewer than 7 completed days in the 14-day baseline period (where a complete day = entry from the evening AND the following morning, i.e. one day will include all the data performed at or after 12.00 in the afternoon up to 12.00 the following morning) then baseline will be set to missing. The baseline for the diary data used in the CompEx analysis will use the same rules. The baseline cough frequency is derived from the cough monitoring performed at Visit 2 (or Rescreening Visit 2 for rescreened participants).

# 3.1.2 Study day

Whenever data is summarised over time, study day will be calculated based on the actual assessment date. All data will be summarised in relation to date of first IP administration.

If actual assessment date is prior to the first IP administration, then study day will be:

Study day = Actual assessment date – first IP administration date.

If actual assessment date is on or after the first IP administration, then study day will be:

Study day = Actual assessment date – first IP administration date + 1.

# 3.1.3 Absolute and percent change from baseline

Absolute and percent change from baseline will be derived as follows:

Absolute change from baseline outcome variables = (post-randomization value – baseline value).

Percent change from baseline = ((post-randomization value – baseline value) / baseline value) × 100.

For any variable subjected to log transformation, the change from baseline calculated and summarised on the log scale will be back transformed and presented as a 'baseline scaled ratio' (BSR). Percentage change will then be calculated as (BSR - 1) x 100.

If either the post-randomization value or the baseline value is missing, then the change from baseline value will also be set to missing.

Percentage change from baseline will not be calculated or presented for variables that may take 0 as a value at baseline.

# 3.1.4 Handling of missing data

No imputation for missing efficacy endpoints will be done. For the primary analysis, MMRM will be used and which, in the event of missing data, uses all data that are available.

Missing safety data will generally not be imputed. However, safety assessment values of the form of "< x" (below the lower limit of quantification) will be imputed as "0.5x LLOQ" in the calculation of summary statistics but displayed as "< x" in the listings. No imputation will be done for laboratory values of the form ">x" (above the upper limit of quantification) and the value ">x" will be displayed in the listings. Note that 0 should not be used as an imputed value in case the endpoint requires a log transformation.

In the different analyses performed, the log-transform eosinophil value can be used, a constant of 0.005 will be added to all the patients at the time of the calculation of the log eosinophil to avoid the issues due to the log-transformation.

Additionally, adverse events that have missing causality (after data querying) will be assumed to be related to study drug.

Missing ADA result at baseline data will be assumed to be negative, for other missing ADA data, no imputation is planned.

PK serum concentrations below the lower limit of quantification will be reported as NQ (Not Quantifiable) in the listings with the LLOQ defined in the footnotes of the relevant TFLs. Individual serum concentrations that are Not Reportable will be reported as NR and those that are missing will be reported as NS (No Sample) in the listings. PK serum concentrations that are NQ, NR or NS will be handled as follows for the provision of descriptive statistics:

- Any values reported as NR or NS will be excluded from the summary tables and corresponding figures.
- At a time point where less than or equal to 50% of the concentration values are NQ, all NQ values will be set to the LLOQ, and all descriptive statistics will be calculated accordingly.

- At a time point where more than 50% (but not all) of the values are NQ, the gmean, gmean  $\pm$  gSD and gCV% will be set to NR. The maximum value will be reported from the individual data, and the minimum and median will be set to NQ.
- If all concentrations are NQ at a time point, no descriptive statistics will be calculated for that time point. The gmean, minimum, median and maximum will be reported as NQ and the gCV% and gmean  $\pm$  gSD as NR.
- The number of values below LLOQ (n < LLOQ) will be reported for each time point together with the total number of collected values (n).

Three observations > LLOQ are required as a minimum for a PK serum concentration to be summarised. Two observations > LLOQ are presented as minimum and maximum with the other summary statistics as NC.

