#### 4.2.10.3 Analysis of laboratory measurements

Laboratory evaluations (continuous haematology, clinical chemistry, urinalysis and coagulation results as per Table 22) will be summarised with descriptive statistics at each visit and change from baseline summarised for each post-baseline visit. Categorical urinalysis results will be summarised in shift tables comparing maximum value during treatment to baseline value. Shifts from baseline to maximum value during treatment in haematology, clinical chemistry, urinalysis and coagulation results will be presented using low, normal and high categories. Laboratory measurements will also be summarised based on the number and percentage of participants above or below a pre-specified threshold for each test, and a listing on key participant information supporting the summary will be provided.

Continuous haematology, clinical chemistry, urinalysis and coagulation results baseline versus maximum observation on treatment will be presented in figures using shift plots.

In addition to the summaries above also the maximum on-treatment ALT and AST by maximum total bilirubin for assessing Hy's law criteria will be presented using the following categories:

Liver Function Parameters	Category
	• $\geq 3 \times - < 5 \times ULN$
ALT	• $\geq 5 \times - <10 \times \text{ULN}$
	• $\geq 10 \times \text{ULN}$
	• $\geq 3 \times - < 5 \times \text{ULN}$
AST	• $\geq 5 \times - <10 \times \text{ULN}$
	• $\geq 10 \times ULN$
T = 4 = 1 1 ; 11;1 ;	• $<2 \times ULN$
l otal bilirubin	• $\geq 2 \times \text{ULN}$
Potential Hy's law	• (AST $\ge$ 3 × ULN or ALT $\ge$ 3 × ULN) and (Total Bilirubin $\ge$ 2×ULN) a

Fable 25	Category for Liver Function parameters
----------	---

ULN: upper limit of normal range.

a: It includes all subjects who have ALT or AST $\ge$ 3xULN and total bilirubin  $\ge$ 2xULN, and in which the elevation in transaminases precede or coincide with (that is, on the same day as) the elevation in total bilirubin.

ALT or AST versus total bilirubin, expressed as multiples of ULN as well as liver biochemistry test results over time – participants with elevated ALT or AST, and elevated total bilirubin will be presented in figures. Liver biochemistry results over time will be presented in figures for participants with elevated AST or ALT, and elevated total bilirubin. A separate listing of key information for participants with potential Hy's law will be produced.

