## 4.2.10.6 Other safety tests

NT-proBNP results will be summarised with descriptive statistics at each visit and change from baseline summarised for each post-baseline visit. The summary based on the number and percentage of participants above or below a pre-specified threshold will be produced. NT-proBNP results will be also summarised in shift table comparing maximum value during treatment to baseline value. NT-proBNP results will be listed.

Number and proportion of participants with a negative or positive SARS-Cov-2 serology result at the end of study, who were seronegative at baseline, will be summarised. Number and proportion of participants who received a COVID-19 vaccine during the study will be included in the summary. All SARS-Cov-2 tests results (both PCR and serology) by visit will be listed for As-treated population.

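### SAP 3.1.4 gives laboratory results below the assay range a number but gives none to results above it, so numeric safety summaries can lose their highest readings

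*SAP*

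**What the plan says.** SAP 3.1.4 (Handling of missing data) opens its safety paragraph with a general default of not imputing missing safety data, and then makes an exception. A result below the lower limit "will be imputed as '0.5x LLOQ' in the calculation of summary statistics but displayed as '< x' in the listings". The next sentence deals with the upper end: "No imputation will be done for laboratory values of the form '>x' (above the upper limit of quantification". Its only other provision is that listings show such a result as it was reported. Nothing more is said about results above the range.

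The outputs that use these data are in three places:
- SAP 4.2.10.3: continuous laboratory results "will be summarised with descriptive statistics at each visit and change from baseline summarised for each post-baseline visit". "Shifts from baseline to maximum value during treatment in haematology, clinical chemistry, urinalysis and coagulation results will be presented", and these "will be presented using low, normal and high categories". The section also plans counts above or below a pre-specified threshold, plots of baseline against maximum on treatment, and figures of ALT and AST against bilirubin in multiples of ULN.
- SAP 4.2.10.6: NT-proBNP gets by-visit statistics, change from baseline and a threshold summary, and "NT-proBNP results will be also summarised in shift table comparing maximum value during treatment to baseline value".
- SAP 3.1.3, on change from baseline: "If either the post-randomization value or the baseline value is missing, then the change from baseline value will also be set to missing".

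**The concern.** The rule is one-sided. A result below the range receives a number and enters the summaries. A result above the range receives none, and the section discusses it only as something to display. For analytes where a high value is the safety signal, the record left without a number is the most extreme one.

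NT-proBNP shows why this matters. It is a named safety endpoint, and Protocol Table 4 lists it among the mitigations for the potential risk of progression of heart failure. SAP 3.8.6 schedules it only at SV1, SV8, SV12 and early discontinuation. A participant who completes treatment therefore has two scheduled post-baseline values, and losing one removes half the basis for that participant's maximum. Liver enzymes are similar, because the planned figures divide the value by its ULN.

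**Working it through.** **No stated figure to reproduce.** The documents give no upper assay limits and no expected number of >x results. The check is therefore mainly a comparison of text, followed by an illustration on stated assumptions.

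**Step 1: which outputs need a number?**

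| Output | Source | Can >x enter without a number? |
|---|---|---|
| Mean, SD and other numeric statistics by visit | SAP 4.2.10.3, 4.2.10.6 | No |
| Change from baseline | SAP 3.1.3, 4.2.10.3, 4.2.10.6 | No; missing if >x is held as missing |
| Numeric maximum on treatment; shift plots | SAP 4.2.10.3; Appendix A, Figures 14.3.7.1 to 14.3.7.4 | No |
| ALT or AST against bilirubin as multiples of ULN | Appendix A, Figures 14.3.7.5 and 14.3.7.6 | No; the multiple is the value divided by ULN |
| Low/normal/high shift tables | SAP 4.2.10.3 | Yes, as high, if x is at or above the upper reference limit |
| Counts above a threshold | SAP 4.2.10.3, 4.2.10.6 | Yes, if the threshold is at or below x |
| Listings | SAP 3.1.4 | Yes, stated |

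**Step 2: one participant (invented values).** Take NT-proBNP of 100 at baseline, 300 at Week 12 and >x at Week 28, with x above 300. If >x is held as missing, the numeric maximum on treatment is 300 and the Week 28 change is missing. With >x set to x, the maximum is x and the change is x − 100, each a lower bound for the truth.

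**Step 3: possible effect on a visit mean (assumed, not from the documents).** Let the marker be lognormal with log-SD s = 0.8 and median 1, let a share q of results lie above the limit, and let z be the (1 − q) normal quantile. Then the limit is u = exp(sz), and the true mean is m = exp(s²/2) = exp(0.32) = 1.377.
- Mean with >x dropped, relative to m: Φ(z − s)/(1 − q)
- Mean with >x set to x, relative to m: Φ(z − s) + q·u/m

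For q = 1%: z = 2.326, u = 6.431 and Φ(1.526) = 0.9365. Dropped: 0.9365/0.99 = 0.946, which is 5.4% too low. Set to x: 0.9365 + 0.01 × 6.431/1.377 = 0.983, which is 1.7% too low.

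| q | Expected >x among 72 (72q) | Mean if dropped | Mean if set to x |
|---|---|---|---|
| 0.5% | 0.36 | −3.3% | −0.9% |
| 1% | 0.72 | −5.4% | −1.7% |
| 5% | 3.6 | −15.7% | −6.4% |

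Both methods err downward. Setting to x errs less at each assumed share.

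**Step 4: threshold counts.** Suppose 5% of 72 participants exceed a threshold (3.6 expected) and 1% are above the assay limit. If the count is derived from the numeric result and >x is missing, 72 × (0.05 − 0.01) = 2.88 are counted. If >x is classed as above the threshold, all 3.6 are counted and no imputation is needed.

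**The case against.** A reader might infer that the SAP removes >x results from every calculation, including shift tables and threshold counts. The documents do not support that. No imputation is not the same as exclusion, and where this SAP means exclusion it says so: for PK values that are not reportable or have no sample (3.1.4), and for cough recordings under 18 hours (3.3.3). Low/normal/high tables and threshold counts are categorical and can place >x correctly without a number. This part of the objection stands, and it confines the certain gap to the numeric outputs.

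A reader might also infer that the rule keeps reassuring values and discards alarming ones. That is not general. For haemoglobin, platelets, leukocytes and albumin the low end is also a safety concern, and those results are kept.

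Third, large distortions of a mean are easy to construct but rest on invented limits and counts. With an assumed lognormal of median 120 and geometric SD 2.5, the expected number above 5,000 among 72 participants is 72 × [1 − Φ(ln(5,000/120)/ln 2.5)] = 72 × [1 − Φ(4.07)] = 0.0017. An example that places even one such result in the arm contradicts its own distribution.

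Finally, extreme values stay visible. All laboratory and NT-proBNP results are listed. The protocol asks for repeats of clinically significant abnormal results (8.2.6) and provides central-laboratory alerts for raised liver tests (Appendix E). Heart failure is also followed through LVEF, cardiac adverse events of special interest, stopping criteria and unblinded DSMB review. So a reader should not conclude that a heart-failure or liver signal would go unseen. What these safeguards do not settle is what number the summary tables and figures use.

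**Conclusion.** The point holds for the numeric outputs. SAP 3.1.4 gives a number to results below the range and specifies none for results above it, so followed as written, >x cannot enter by-visit means, changes from baseline, numeric maxima, shift plots or ULN-multiple figures. If it is held as missing, the highest readings are lost and those summaries err downward. Whether categorical shift tables and threshold counts are touched depends on programming that the SAP does not describe.

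The size cannot be derived from the documents. It is probably small, and nil if over-range samples are diluted and re-assayed, on which the documents are silent. The percentages above rest on an assumed lognormal with log-SD 0.8 and assumed shares above the limit. They show direction and relative merit, not an estimate for this trial. No efficacy analysis, alpha or sample-size figure is involved. This is a cheap improvement, not a flaw that threatens the safety conclusions.

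**What to change.** In SAP 3.1.4, replace the sentence on results above the upper limit with a rule along these lines: a laboratory result reported as >x is set to x for summary statistics, change from baseline and maximum on treatment; it is classed as high where x is at or above the upper reference limit, and as above any threshold at or below x; it is shown as >x in listings, and each affected table or figure footnotes the number of such results.

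The cost is a short SAP edit and a small amount of programming. The downside is that x is a lower bound, so summaries that use it slightly understate the true values. That is still closer than leaving the records out, and the footnoted count shows the reader where it applies.
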